12.1.3 Safety Assessments

Safety assessments will consist of monitoring and recording all AEs, including all CTCAE v 4.0 grades (for both increasing and decreasing severity) and SAEs; regular laboratory evaluation for hematology, blood chemistry, and urine values; periodic measurement of vital signs; and the performance of physical examinations.

12.2 Response Criteria for Patients with Solid Tumors

See the table in [section 8.0](#) for the schedule of tumor evaluations. In addition to the scheduled scans, a confirmatory scan should be obtained the next consecutive cycle following initial documentation of objective response.

Response and progression will be evaluated in this study using the revised Response Evaluation Criteria in Solid Tumors (RECIST) guideline (version 1.1) [Eur J Ca 45:228-247, 2009]. Key points are that 5 target lesions are identified and that changes in the *largest* diameter (unidimensional measurement) of the tumor lesions but the *shortest* diameter of malignant lymph nodes are used in the RECIST v 1.1 criteria.

12.2.1 Definitions

12.2.1.1 Evaluable for objective response: Patients who exhibit objective disease progression prior to the end of cycle 1 will be considered evaluable for response. For all other patients, only those patients who have measurable disease present at baseline, have received at least one cycle of therapy, and have had their disease re-evaluated will be considered evaluable for response.

12.2.1.2 **Evaluable Non-Target Disease Response:** Patients who have lesions present at baseline that are evaluable but do not meet the definitions of measurable disease, have received at least one cycle of therapy, and have had their disease re-evaluated will be considered evaluable for non-target disease. The response assessment is based on the presence, absence, or unequivocal progression of the lesions.

12.2.2 **Disease Parameters**

12.2.2.1 **Measurable disease:** Measurable lesions are defined as those that can be accurately measured in at least one dimension (longest diameter to be recorded) as ≥ 20 mm by chest x-ray, as ≥ 10 mm with CT scan, or ≥ 10 mm with calipers by clinical exam. All tumor measurements must be recorded in millimeters (or decimal fractions of centimeters).

Note: Tumor lesions that are situated in a previously irradiated area might or might not be considered measurable. If the investigator thinks it appropriate to include them, the conditions under which such lesions should be considered must be defined in the protocol.

12.2.2.2 **Malignant lymph nodes:** To be considered pathologically enlarged and measurable, a lymph node must be ≥ 15 mm in short axis when assessed by CT scan (CT scan slice thickness no greater than 5 mm). At baseline and in follow-up, only the short axis will be measured and followed.

12.2.2.3 **Non-measurable disease:** All other lesions (or sites of disease), including small lesions (longest diameter < 10 mm or pathological lymph nodes with ≥ 10 to < 15 mm short axis), are considered non-measurable disease. Bone lesions, leptomeningeal disease, ascites, pleural/pericardial effusions, lymphangitis cutis/pulmonitis, inflammatory breast disease, and abdominal masses (not followed by CT or MRI), are considered as non-measurable.

Note: Cystic lesions that meet the criteria for radiographically defined simple cysts should not be considered as malignant lesions (neither measurable nor non-measurable) since they are, by definition, simple cysts. 'Cystic lesions' thought to represent cystic metastases can be considered as measurable lesions, if they meet the definition of measurability described above. However, if non-cystic lesions are present in the same patient, these are preferred for selection as target lesions.

12.2.2.4 **Target lesions:** All measurable lesions up to a maximum of 2 lesions per organ and 5 lesions in total, representative of all involved organs, should be identified as target lesions and recorded and measured at baseline. Target lesions should be selected on the basis of their size (lesions with the longest diameter), be representative of all involved organs, but in addition should be those that lend themselves to

THIS PROTOCOL IS FOR RESEARCH PURPOSES ONLY, SEE PAGE 1 FOR USAGE POLICY

reproducible repeated measurements. It may be the case that, on occasion, the largest lesion does not lend itself to reproducible measurement in which circumstance the next largest lesion that can be measured reproducibly should be selected. A sum of the diameters (longest for non-nodal lesions, short axis for nodal lesions) for all target lesions will be calculated and reported as the baseline sum diameters. If lymph nodes are to be included in the sum, then only the short axis is added into the sum. The baseline sum diameters will be used as reference to further characterize any objective tumor regression in the measurable dimension of the disease.

12.2.2.5 **Non-target lesions:** All other lesions (or sites of disease) including any measurable lesions over and above the 5 target lesions should be identified as non-target lesions and should also be recorded at baseline. Measurements of these lesions are not required, but the presence, absence, or in rare cases unequivocal progression of each should be noted throughout follow-up.

12.2.3 **Methods for Evaluation of Measurable Disease**

All measurements should be taken and recorded in metric notation using a ruler or calipers.

The same method of assessment and the same technique should be used to characterize each identified and reported lesion at baseline and during follow-up. Imaging-based evaluation is preferred to evaluation by clinical examination unless the lesion(s) being followed cannot be imaged but are assessable by clinical exam.

12.2.3.1 **Clinical lesions:** Clinical lesions will only be considered measurable when they are superficial (e.g., skin nodules and palpable lymph nodes) and ≥ 10 mm diameter as assessed using calipers (e.g., skin nodules). In the case of skin lesions, documentation by color photography, including a ruler to estimate the size of the lesion, is recommended.

12.2.3.2 **Chest x-ray:** Lesions on chest x-ray are acceptable as measurable lesions when they are clearly defined and surrounded by aerated lung. However, CT is preferable.

12.2.3.3 **Conventional CT and MRI:** This guideline has defined measurability of lesions on CT scan based on the assumption that CT slice thickness is 5 mm or less. If CT scans have slice thickness greater than 5 mm, the minimum size for a measurable lesion should be twice the slice thickness. MRI is also acceptable in certain situations (e.g. for body scans). Ideally, the same type of scanner should be used and the image acquisition protocol should be followed as closely as possible to prior scans.

THIS PROTOCOL IS FOR RESEARCH PURPOSES ONLY, SEE PAGE 1 FOR USAGE POLICY

12.2.3.4 **PET-CT:** At present, the low dose or attenuation correction CT portion of a combined PET-CT is not always of optimal diagnostic CT quality for use with RECIST measurements. However, if the site can document that the CT performed as part of a PET-CT is of identical diagnostic quality to a diagnostic CT (with IV and oral contrast), then the CT portion of the PET-CT can be used for RECIST measurements and can be used interchangeably with conventional CT in accurately measuring cancer lesions over time. Note, however, that the PET portion of the CT introduces additional data which may bias an investigator if it is not routinely or serially performed.

12.2.3.5 **Tumor markers:** Tumor markers alone cannot be used to assess response. If markers are initially above the upper normal limit, they must normalize for a patient to be considered in complete clinical response.

12.2.3.6 **Cytology, Histology:** These techniques can be used to differentiate between partial responses (PR) and complete responses (CR) in rare cases (e.g., residual lesions in tumor types, such as germ cell tumors, where known residual benign tumors can remain).

Cytology should be obtained if an effusion appears or worsens during treatment when the measurable tumor has met criteria for response or stable disease.

12.2.3.7 **FDG-PET:** While FDG-PET response assessments need additional study, it is sometimes reasonable to incorporate the use of FDG-PET scanning to complement CT scanning in assessment of progression (particularly possible 'new' disease). New lesions on the basis of FDG-PET imaging can be identified according to the following algorithm:

- a. Negative FDG-PET at baseline, with a positive FDG-PET at follow-up is a sign of PD based on a new lesion.
- b. No FDG-PET at baseline and a positive FDG-PET at follow-up: If the positive FDG-PET at follow-up corresponds to a new site of disease confirmed by CT, this is PD. If the positive FDG-PET at follow-up is not confirmed as a new site of disease on CT, additional follow-up CT scans are needed to determine if there is truly progression occurring at that site (if so, the date of PD will be the date of the initial abnormal FDG-PET scan). If the positive FDG-PET at follow-up corresponds to a pre-existing site of disease on CT that is not progressing on the basis of the anatomic images, this is not PD.

Note: A 'positive' FDG-PET scan lesion means one that is FDG avid with an uptake greater than twice that of the surrounding tissue on the attenuation corrected image.

THIS PROTOCOL IS FOR RESEARCH PURPOSES ONLY, SEE PAGE 1 FOR USAGE POLICY

12.2.4 Response Criteria for Patients with Solid Tumor and Measurable Disease**12.2.4.1 Evaluation of Target Lesions****Complete Response (CR):**

Disappearance of all target and non-target lesions. Any pathological lymph nodes (whether target or non-target) must have reduction in short axis to <10 mm. If immunocytology is available, no disease must be detected by that methodology. Normalization of urinary catecholamines or other tumor markers if elevated at study enrollment (for patients with neuroblastoma).

Partial Response (PR):

At least a 30% decrease in the sum of the diameters of target lesions, taking as reference the baseline sum diameters

Progressive Disease (PD):

At least a 20% increase in the sum of the diameters of target lesions, taking as reference the smallest sum on study (this includes the baseline sum if that is the smallest on study). In addition to the relative increase of 20%, the sum must also demonstrate an absolute increase of at least 5 mm. (Note: the appearance of one or more new lesions is also considered progressions). Note: in presence of SD or PR in target disease but unequivocal progression in non-target or non-measurable disease, the patient has PD if there is an overall level of substantial worsening in non-target disease such that the overall tumor burden has increased sufficiently to merit discontinuation of therapy

Stable Disease (SD):

Neither sufficient shrinkage to qualify for PR nor sufficient increase to qualify for PD, taking as reference the smallest sum diameters while on study

12.2.4.2 Evaluation of Non-Target Lesions**Complete Response (CR):**

Disappearance of all non-target lesions and normalization of tumor marker level. All lymph nodes must be non-pathological in size (<10 mm short axis)

Note: If tumor markers are initially above the upper normal limit, they must normalize for a patient to be considered in complete clinical response.

Non-CR/Non-PD:

Persistence of one or more non-target lesion(s) and/or maintenance of tumor marker level above the normal limits

Progressive Disease (PD):

Appearance of one or more new lesions and/or *unequivocal progression* of existing non-target lesions. *Unequivocal progression* should not normally trump target lesion status. It must be representative of overall disease status change, not a single lesion increase.

12.2.5 Overall Best Response Assessment

Each patient will be classified according to his “best response” for the purposes of analysis of treatment effect. Best response is determined as outlined in [Section 12.7](#) from a sequence of overall response assessments.

12.3 Response Criteria for Patients with Solid Tumors and Evaluable Disease**12.3.1 Evaluable Disease**

The presence of at least one lesion, with no lesion that can be accurately measured in at least one dimension. Such lesions may be evaluable by nuclear medicine techniques, immunocytochemistry techniques, tumor markers or other reliable measures.

12.3.2 Complete Response

Disappearance of all evaluable disease.

12.3.3 Partial response

Partial responses cannot be determined in patients with evaluable disease

12.3.4 Stable Disease (SD)

That which does not qualify as Complete Response (CR), Partial Response (PR), or Progressive Disease.

12.3.5 Progressive Disease

The appearance of one or more new lesions or evidence of laboratory, clinical, or radiographic progression.

12.3.6 Overall Best Response Assessment

Each patient will be classified according to his “best response” for the purposes of analysis of treatment effect. Best response is determined as outlined in [Section 12.7](#) from a sequence of overall response assessments.

12.4 Response Criteria for Neuroblastoma Patients with MIBG Positive Lesions**12.4.1 MIBG Positive Lesions**

Patients who have a positive MIBG scan at the start of therapy will be evaluable for MIBG response. The use of ^{123}I for MIBG imaging is recommended for all scans. If the patient has only one MIBG positive lesion and that lesion was radiated, a biopsy must be done at least 28 days after radiation was completed and must show viable neuroblastoma.

12.4.2 The following criteria will be used to report MIBG response by the treating institution:

Complete response: Complete resolution of all MIBG positive lesions
Partial Response: Resolution of at least one MIBG positive lesion, with persistence of other MIBG positive lesions
Stable disease: No change in MIBG scan in number of positive lesions
Progressive disease: Development of new MIBG positive lesions

[figure not shown]
12.4.3 The response of MIBG lesions will be assessed on central review using the Curie scale¹⁴ as outlined below. Central review responses will be used to assess efficacy for study endpoint. See [Section 8.3.2](#) for details on transferring images to the Imaging Research Center.

NOTE: This scoring should also be done by the treating institution for end of course response assessments.

The body is divided into 9 anatomic sectors for osteomedullary lesions, with a 10th general sector allocated for any extra-osseous lesion visible on MIBG scan. In each region, the lesions are scored as follows. The **absolute extension score** is graded as:

0 = no site per segment,
1 = 1 site per segment,
2 = more than one site per segment,
3 = massive involvement (>50% of the segment).

The **absolute score** is obtained by adding the score of all the segments. See diagram of sectors below:

The **relative score** is calculated by dividing the absolute score at each time point by the corresponding pre-treatment absolute score. The relative score of each patient is calculated at each response assessment compared to baseline and classified as below:

1. **Complete response:** all areas of uptake on MIBG scan completely resolved. If morphological evidence of tumor cells in bone marrow biopsy or

THIS PROTOCOL IS FOR RESEARCH PURPOSES ONLY, SEE PAGE 1 FOR USAGE POLICY

aspiration is present at enrollment, no tumor cells can be detected by routine morphology on two subsequent bilateral bone marrow aspirates and biopsies done at least 21 days apart to be considered a **Complete Response**.

2. **Partial response:** Relative score ≤ 0.2 (lesions almost disappeared) to ≤ 0.5 (lesions strongly reduced).
3. **Stable disease:** Relative score > 0.5 (lesions weakly but significantly reduced) to 1.0 (lesions not reduced).
4. **Progressive disease:** New lesions on MIBG scan.

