8.3 Radiology Studies

8.3.1 Bone Age/Knee MRI

All tibial radiographs and knee MRIs (if obtained) should be submitted for review.

8.3.2 Central Radiology Review for Response: Patients who respond (CR, PR) to therapy or have long term stable disease (SD) (≥ 3 cycles) on protocol therapy will be centrally reviewed. COG Operations Center will notify the Imaging Center of any patient requiring central review. The Imaging Center will then request that the treating institution forward the requested images for central review. The central image evaluation results will be entered into RAVE for review by the COG Operations Center and for data analysis.

The images are to be forwarded electronically to the Imaging Research Center at Children's Hospital Los Angeles via the ImageInBox.

COG institutions that are not connected via the ImageInBox can send the images on hard copy film, CD ROM, USB flash drive or by FTP. Submitted imaging studies should be clearly marked with the COG patient ID, study number (ADVL1416) and date and shipped to [name] at the address below:

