12.7 Best Response**12.7.1 Evaluation of Best Overall Response**

The best overall response is the best response recorded from the start of the treatment until disease progression/recurrence (taking as reference for progressive disease the smallest measurements recorded since the treatment started). The patient's best response assignment will depend on the achievement of both measurement and confirmation criteria.

Table 1: For Patients with Measurable Disease (i.e., Target Disease)

Target	Non-Target	New	Overall	Best Overall Response
--------	------------	-----	---------	-----------------------

THIS PROTOCOL IS FOR RESEARCH PURPOSES ONLY, SEE PAGE 1 FOR USAGE POLICY

Lesions	Lesions	Lesions	Response	when Confirmation is Required*
CR	CR	No	CR	≥ 28 days Confirmation
CR	Non-CR/Non-PD	No	PR	≥ 28 days Confirmation
CR	Not evaluated	No	PR	
PR	Non-CR/Non-PD/not evaluated	No	PR	
SD	Non-CR/Non-PD/not evaluated	No	SD	documented at least once ≥ 28 days from baseline
PD	Any	Yes or No	PD	no prior SD, PR or CR
Any	PD**	Yes or No	PD	
Any	Any	Yes	PD	

* See RECIST 1.1 manuscript for further details on what is evidence of a new lesion.
** In exceptional circumstances, unequivocal progression in non-target lesions may be accepted as disease progression.

Note: Patients with a global deterioration of health status requiring discontinuation of treatment without objective evidence of disease progression at that time should be reported as "symptomatic deterioration." Every effort should be made to document the objective progression even after discontinuation of treatment.

Table 2: For Patients with Non-Measurable Disease (i.e., Non-Target Disease)

Non-Target Lesions	New Lesions	Overall Response
CR	No	CR
Non-CR/non-PD	No	Non-CR/non-PD*
Not all evaluated	No	not evaluated
Unequivocal PD	Yes or No	PD
Any	Yes	PD

* 'Non-CR/non-PD' is preferred over 'stable disease' for non-target disease since SD is increasingly used as an endpoint for assessment of efficacy in some trials so to assign this category when no lesions can be measured is not advised

Table 3. Sequences of overall response assessments with corresponding best response.

1 st Assessment	2 nd Assessment	Best Response
Progression		Progressive disease
Stable, PR, CR	Progression	Progressive disease
Stable	Stable	Stable
Stable	PR, CR	Stable
Stable	Not done	Not RECIST classifiable
PR	PR	PR
PR	CR	PR
PR, CR	Not done	Not RECIST classifiable
CR	CR	CR

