### 6.5. Efficacy Analyses

#### 6.5.1. Efficacy Analysis Variables

Definition of efficacy analysis variables are listed below:

- **Objective response rate (ORR)** is defined as the proportion of treated patients achieving a best overall response of partial response (PR) or complete response (CR) per Response Evaluation Criteria in Solid Tumors Version 1.1(RECIST v.1.1). Patients who do not have any postbaseline tumor response assessments for any reason are considered nonresponders and are included in the denominator when calculating the response rate.
- **Disease control rate (DCR)** is defined as the proportion of treated patients achieving a best overall response of CR, PR, or stable disease (SD) per RECIST v.1.1. Patients who do not have any postbaseline tumor response assessments for any reason are considered non-responders and are included in the denominator when calculating the response rate.
- **Duration of response (DOR)** is defined from the date of first documented CR or PR (responder) to the date of objective progression or the date of death due to any cause, whichever is earlier. If a responder is not known to have died or have objective progression, then the patient will be censored at the date of last evaluable tumor assessment.
- **Progression-free survival (PFS)** is defined as the time from the date of randomization until the date of radiographic documentation of progression (as defined by RECIST v. 1.1) based on investigator assessment or the date of death due to any cause, whichever is earlier. The censoring is taken in the following order:
  - If a patient does not have a baseline disease assessment, then the PFS time will be censored at the randomization date, regardless of whether or not objective progressive disease (PD) or death has been observed for the patient.
  - If a patient is not known to have died or have investigator-assessed PD as of the data-inclusion cut-off date for the analysis, the PFS time will be censored at the date of last postbaseline adequate radiological tumor assessment, or at the date of randomization if the patient does not have any postbaseline adequate radiological assessment.

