### **6.5.2. *Description of Efficacy Analyses***

Best overall response is the best response recorded from the start of treatment until disease progression, in the order of CR, PR, and SD. Best overall response will be summarized for all patients evaluable for efficacy whose disease is assessable by RECIST 1.1.

If appropriate, the following analyses will be performed.

- Objective response rate will be estimated and reported for each dose level.
- Disease control rate will be summarized and provided for each dose level.

- Progression-free survival will be estimated using a Kaplan-Meier method (Kaplan and Meier 1958) by median and 95% confidence interval (CI). Additional exploratory analyses using proportional hazards models to control for other factors may be performed.
- Overall survival will be summarized using the Kaplan-Meier method.

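### The SAP's best response rule omits the protocol's confirmation requirement and central review, so an unconfirmed site-called response could count in ORR

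*Protocol*

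**What the plan says.** **Protocol, confirmation.** Section 12.7.1 states that the patient's "best response assignment will depend on the achievement of both measurement and confirmation criteria". Table 1 there gives an interval of at least 28 days. Section 12.2 supplies the visit: "a confirmatory scan should be obtained the next consecutive cycle following initial documentation of objective response".

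**Protocol, central review.** Section 8.3.2 sends patients with CR, PR, or stable disease lasting at least three cycles to central review, and continues: "The central image evaluation results will be entered into RAVE for review by the COG Operations Center and for data analysis". For MIBG-positive neuroblastoma, 12.4.3 has the central reader apply the Curie scale and says "Central review responses will be used to assess efficacy for study endpoint".

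**SAP.** Section 6.5.2 has its own rule: "Best overall response is the best response recorded from the start of treatment until disease progression, in the order of CR, PR, and SD". It limits the summary of best response to disease assessable by RECIST 1.1. Section 6.5.1 defines ORR as the proportion of treated patients whose best response is PR or CR by RECIST v1.1. The only assessor named is in the definition of PFS: "radiographic documentation of progression (as defined by RECIST v. 1.1) based on investigator assessment". Neither section mentions confirmation, central review, MIBG or the Curie scale.

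**The concern.** The two documents give different rules for who is a responder. The SAP's rule is the more generous one, because a single recorded PR or CR satisfies it. The trial is open-label (Protocol 5.1) and has no control arm, so a response called at the site and never repeated is the version most open to optimism.

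ORR, disease control rate (DCR) and duration of response (DOR) all depend on best response or on the date of first response. If the assessor and the confirmation rule are not fixed in the SAP, the choice can be made after the responses are known. In cohorts this small, one patient can separate reporting a response from reporting none.

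A second gap is separate. The protocol gives central MIBG response a role in the efficacy assessment, and the SAP has no place where it is analysed.

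**Working it through.** No sample size, power or error rate rests on ORR, so there is no planned figure to reproduce. The check compares the texts and then sizes the effect of one patient.

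**Step 1. Same patient, two rules.** Three sequences from Protocol 12.7.1 Table 3, set against the SAP wording taken literally:

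| First assessment | Second assessment | SAP 6.5.2 | Protocol Table 3 |
|---|---|---|---|
| PR | Not done | PR | Not RECIST classifiable |
| PR | Progression | PR | Progressive disease |
| Stable | PR | PR | Stable |

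Each row adds one to the SAP's ORR numerator and nothing under the protocol. Table 3 covers only two assessments. It does not say what happens to a patient who is stable, then PR, then PR again.

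**Step 2. Is confirmation feasible on the planned schedule?** A cycle is 42 days (Protocol 5.1), and the confirmatory scan falls in the next cycle (12.2). Since 42 > 28, the planned scan satisfies the Table 1 interval without extra imaging. In the table as extracted, the 28-day entry stands beside the CR row and the first PR row. I take the blank PR cells below it as covered by the same entry.

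**Step 3. Effect of one reclassified responder.** The change in ORR is 1/n. The documents do not give the final efficacy denominator, so n is an assumption:

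- n = 6, a full rolling-six cohort: 1/6 = 16.7 points
- n = 12, the evaluable patients in the RP2D rule (Protocol 11.2.3): 1/12 = 8.3 points
- n = 24, the anticipated maximum evaluable in Part A (Protocol 11.1): 1/24 = 4.2 points
- n = 29, Part A enrolment allowing for inevaluable patients (Protocol 11.1): 1/29 = 3.4 points

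At n = 12, the exact (Clopper-Pearson) 95% intervals are 0.2% to 38.5% for 1/12 and 0% to 26.5% for 0/12. The intervals overlap heavily; what changes is whether any response is reported.

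**Step 4. MIBG rules.** At the site, 12.4.2 defines PR as "Resolution of at least one MIBG positive lesion, with persistence of other MIBG positive lesions". Centrally, 12.4.3 requires a relative score (follow-up score divided by baseline score) of at most 0.5. With one site in each involved sector and one lesion resolved:

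- 10 sectors: 9/10 = 0.9, site PR, central stable disease
- 4 sectors: 3/4 = 0.75, site PR, central stable disease
- 2 sectors: 1/2 = 0.5, PR under both

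The two rules can therefore disagree even when the readers agree on the scan. Whether this reaches ORR is taken up under the objection.

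**The case against.** **The SAP may simply be relying on the protocol.** SAP 6.5.2 closely follows the opening sentence of Protocol 12.7.1, the confirmation requirement is in the same paragraph of the protocol, and nothing in the SAP revokes it. This stands in part: silence is not a decision to drop the central reads or the confirmation rule. However, where the SAP leans on the protocol it says so, as for the DLT definition (6.7) and performance level (6.3). For best response it writes its own definition and cites nothing in 12.7.

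**A reader might infer that ORR will rest on unconfirmed site calls.** The documents do not support that. The investigator is named for PFS only, and ORR has no assessor. The most the text allows is that ORR could rest on such calls.

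**A reader might infer that generous site MIBG calls inflate ORR.** They do not, on the wording. The SAP's ORR is defined by RECIST v1.1 and best response is limited to RECIST-assessable disease. Even under the protocol, Table 4 in 12.7.1 gives overall stable disease when CT/MRI is stable, whatever the MIBG improvement. Sites are also asked, in the note in 12.4.3, to do the Curie scoring themselves. The MIBG defect is a missing analysis.

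**Adopting 12.7.1 whole would do harm.** This stands. Taken literally, the Table 3 row for stable followed by PR or CR would discard late responders.

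**Central review is not a full independent assessment.** This also stands. It is triggered by site-called CR or PR or by long stable disease, so progression and short stable disease are never read centrally.

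**Little depends on ORR.** This stands too. Antitumor activity is a secondary, preliminary aim (Protocol 1.2), response is reported descriptively (11.5), and SAP 6.5.2 makes ORR conditional on being appropriate. The MTD and RP2D rest on DLTs and trough concentration.

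**Conclusion.** The point holds in limited form. The SAP's written rule for best response has no confirmation condition and its ORR has no named assessor, while the protocol requires confirmation and sends central reads to the analysis. Taken literally, the SAP counts some patients as responders whom the protocol would not.

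One such patient moves ORR by 16.7 points at n = 6 and 3.4 points at n = 29. Those denominators are assumptions, and the documents give no basis for predicting how many patients would be affected. Separately, the protocol's central Curie-based MIBG response has no analysis in the SAP.

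Severity is low to moderate. No test, sample size or dose decision is touched.

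**What to change.** In SAP 6.5.1 and 6.5.2:

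- Count a CR or PR in ORR only if it is confirmed at least 28 days later (Protocol 12.7.1 Table 1) and upheld on the central review of 8.3.2.
- Report site-assessed ORR beside it, with the number of discordant patients. Say in advance how a long stable disease that the central reader calls a response is shown.
- State that a first response after stable disease counts if it is later confirmed, and reconcile this with the stable-then-PR/CR row of Protocol Table 3.
- Apply the same responder definition to DOR.
- Report central Curie-based MIBG response as its own descriptive summary, outside the RECIST ORR.
- Leave PFS and DCR on site assessment, and say so, because progression and short stable disease are not centrally read.

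The cost is SAP wording, the reconciliation of one protocol table row, one extra column and one small summary. The scans and central reads are already planned. The downside is that ORR may be slightly lower.
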